**RO7049389—F. Hoffmann-La Roche Ltd**  
56/Protocol YP39406, Version 4

### **5.2.5.6        Abnormal Liver Function Tests**

The finding of an elevated ALT or AST ( $\geq 3 \times \text{ULN}$ ) in combination with either an elevated total bilirubin ( $\geq 2 \times \text{ULN}$ ) or clinical jaundice in the absence of cholestasis or other causes of hyperbilirubinemia is considered to be an indicator of severe liver injury. Therefore, investigators must report as an adverse event the occurrence of either of the following:

- Treatment-emergent ALT or AST  $> 3 \times \text{ULN}$  in combination with total bilirubin  $> 2 \times \text{ULN}$ .
- Treatment-emergent ALT or AST  $> 3 \times \text{ULN}$  in combination with clinical jaundice.

The most appropriate diagnosis or (if a diagnosis cannot be established) the abnormal laboratory values should be recorded on the Adverse Event eCRF (see Section 5.2.5.1) and reported to the Sponsor immediately (i.e., no more than 24 hours after learning of the event), either as a serious adverse event or a non-serious adverse event of special interest (see Section 5.3.2) and to the local health authority and IRB/EC, if required by local requirements.

### **5.2.5.7        Deaths**

All deaths that occur during the protocol-specified adverse event reporting period (see Section 5.2.1), regardless of relationship to study drug, must be recorded on the Adverse Event eCRF and immediately reported to the Sponsor (see Section 5.4.2).

Death should be considered an outcome and not a distinct event. The event or condition that caused or contributed to the fatal outcome should be recorded as the single medical concept on the Adverse Event eCRF. Generally, only one such event should be reported. The term “sudden death” should only be used for the occurrence of an abrupt and unexpected death due to presumed cardiac causes in a subject with or without preexisting heart disease, within 1 hour of the onset of acute symptoms or, in the case of an unwitnessed death, within 24 hours after the subject was last seen alive and stable. If the cause of death is unknown and cannot be ascertained at the time of reporting, “unexplained death” should be recorded on the Adverse Event eCRF. If the cause of death later becomes available (e.g., after autopsy), “unexplained death” should be replaced by the established cause of death.

### **5.2.5.8        Preexisting Medical Conditions**

A preexisting medical condition is one that is present at the screening visit for this study. Such conditions should be recorded on the General Medical History and Baseline Conditions eCRF.

A preexisting medical condition should be recorded as an adverse event only if the frequency, severity, or character of the condition worsens during the study. When recording such events on the Adverse Event eCRF, it is important to convey the concept that the preexisting condition has changed by including applicable descriptors (e.g., “more frequent headaches”).

**RO7049389—F. Hoffmann-La Roche Ltd**  
57/Protocol YP39406, Version 4

### **5.2.5.9 Hospitalization or Prolonged Hospitalization**

Any adverse event that results in hospitalization or prolonged hospitalization should be documented and reported as a serious adverse event (per the definition of serious adverse event in Section 5.2.5.9), except as outlined below.

The following hospitalization scenarios are not considered to be serious adverse events:

- Hospitalization for respite care.
- Planned hospitalization required by the protocol (e.g., for study drug administration and intensive PK sampling).
- Hospitalization for a preexisting condition, provided that all of the following criteria are met:

The hospitalization was planned prior to the study or was scheduled during the study when elective surgery became necessary because of the expected normal progression of the disease.

The study subject has not suffered an adverse event.

The following hospitalization scenarios are not considered to be serious adverse events, but should be reported as adverse events instead:

- Hospitalization for an adverse event that would ordinarily have been treated in an outpatient setting had an outpatient clinic been available

### **5.2.5.10 Overdoses**

Study drug overdose is the accidental or intentional use of the drug in an amount higher than the dose being studied. An overdose or incorrect administration of study drug is not an adverse event unless it results in untoward medical effects.

Any study drug overdose or incorrect administration of study drug should be noted on the Study Drug Administration eCRF.

All adverse events associated with an overdose or incorrect administration of study drug should be recorded on the Adverse Event eCRF. If the associated adverse event fulfills serious criteria, the event should be reported to the Sponsor immediately (i.e., no more than 24 hours after learning of the event; see Section 5.3.2) and to the local health authority and IRB/EC, if required by local requirements.

## **5.3 IMMEDIATE REPORTING REQUIREMENTS FROM INVESTIGATOR TO SPONSOR**

Certain events require immediate reporting to allow the Sponsor to take appropriate measures to address potential new risks in a clinical trial. The Investigator must report such events to the Sponsor immediately; under no circumstances should reporting take place more than 24 hours after the investigator learns of the event. The following is a list

**RO7049389—F. Hoffmann-La Roche Ltd**  
58/Protocol YP39406, Version 4

of events that the Investigator must report to the Sponsor within 24 hours after learning of the event, regardless of relationship to study drug:

- Serious adverse events
- Non-serious adverse events of special interest
- Pregnancies (see Section 5.3.3)

The Investigator must report new significant follow-up information for these events to the Sponsor immediately (i.e., no more than 24 hours after becoming aware of the information). New significant information includes the following:

- New signs or symptoms or a change in the diagnosis
- Significant new diagnostic test results
- Change in causality based on new information
- Change in the event's outcome, including recovery
- Additional narrative information on the clinical course of the event

Investigators must also comply with local requirements for reporting serious adverse events to the local health authority and IRB/EC.

### **5.3.1 Emergency Medical Contacts**

To ensure the safety of Study Subjects, access to the Medical monitors is available 24 hours a day 7 days a week. Medical monitors contact details are listed in the "Protocol Administrative and Contact Information & List of Investigators".

### **5.3.2 Reporting Requirements for Serious Adverse Events and Non-Serious Adverse Events of Special Interest**

#### **Events that Occur prior to Study Treatment Initiation**

After informed consent has been obtained but prior to initiation of study treatment, only serious adverse events caused by a protocol-mandated intervention should be reported. The Serious Adverse Event/Adverse Event of Special Interest Reporting Form provided to Investigators should be completed and submitted to the Serious Adverse Event Responsible immediately (i.e., no more than 24 hours after learning of the event).

## **Events that Occur after Study Treatment Initiation**

For reports of serious adverse events and non-serious adverse events of special interest (see Section 5.1.2 and 5.1.3) that occur after initiation of study treatment until the end of the adverse event reporting period (defined in Section 5.5), investigators should record all case details that can be gathered immediately (i.e., within 24 hours after learning of the event) on the appropriate Adverse Event of Special Interest/ Serious Adverse Event eCRF form and submit the report via the electronic data capture (EDC) system. A report will be generated and sent to the Sponsor's Safety Risk Management department.

In the event that the EDC system is unavailable, the Serious Adverse Event/Adverse Event of Special Interest Reporting Form provided to investigators should be completed and submitted to the Serious Adverse Event Responsible immediately (i.e., no more than 24 hours after learning of the event) and to the local health authority and IRB/EC, if required by local requirements.

Once the EDC system is available, all information will need to be entered and submitted via the EDC system.

### **5.3.3 Reporting Requirements for Pregnancies**

#### **5.3.3.1 Pregnancies in Female Subjects**

Female subjects of childbearing potential will not be allowed to participate in this study. However, if a female subject becomes pregnant during the study or within 28 days after the last dose of study drug, a Clinical Trial Pregnancy Reporting Form should be completed by the investigator and submitted to the sponsor within 24 hours after learning of the pregnancy. Pregnancy should not be recorded on the Adverse Event eCRF. The Investigator should discontinue study drug and counsel the subject, discussing the risks of the pregnancy and the possible effects on the fetus. Monitoring of the subject should continue until conclusion of the pregnancy.

#### **5.3.3.2 Pregnancies in Female Partners of Male Study Subjects**

Male Subjects will be instructed through the Informed Consent Form to immediately inform the Investigator if their partner becomes pregnant during the study or within 28 days after the last dose of study drug. A Clinical Trial Pregnancy Reporting Form should be completed by the Investigator and submitted to the Sponsor within 24 hours after learning of the pregnancy. Attempts should be made to collect and report details of the course and outcome of any pregnancy in the partner of a male study subject exposed to study drug. The pregnant partner will need to sign an Authorization for Use and Disclosure of Pregnancy Health Information to allow for follow-up on her pregnancy. Once the authorization has been signed, the Investigator will update the Clinical Trial Pregnancy Reporting Form with additional information on the course and outcome of the pregnancy. An Investigator who is contacted by the male study subject or his pregnant partner may provide information on the risks of the pregnancy and the possible effects

**RO7049389—F. Hoffmann-La Roche Ltd**  
60/Protocol YP39406, Version 4

on the fetus, to support an informed decision in cooperation with the treating physician and/or obstetrician.

#### **5.3.3.3      Abortions**

Any spontaneous abortion should be classified as a serious adverse event (as the Sponsor considers spontaneous abortions to be medically significant events), recorded on the Adverse Event eCRF, and reported to the Sponsor immediately (i.e., no more than 24 hours after learning of the event; see Section 5.3.2) and to the local health authority and IRB/EC, if required by local requirements.

Any induced abortion due to maternal toxicity and/or embryo-fetal toxicity should also be classified as serious adverse event, recorded on the Adverse Event eCRF, and reported to the Sponsor immediately (i.e., no more than 24 hours after learning of the event; see Section 5.3.2) and to the local health authority and IRB/EC, if required by local requirements.

Elective abortion not associated with toxicity (e.g., induced abortion for personal reasons) does not require expedited reporting but should be reported as outcome of pregnancy on the Clinical Trial Pregnancy Reporting Form.

#### **5.3.3.4      Congenital Anomalies/Birth Defects**

Any congenital anomaly/birth defect in a child born to a female subject or female partner of a male subject exposed to study drug should be classified as a serious adverse event, recorded on the Adverse Event eCRF, and reported to the Sponsor immediately (i.e., no more than 24 hours after learning of the event; see Section 5.3.2) and to the local health authority and IRB/EC, if required by local requirements.

### **5.4           FOLLOW-UP OF SUBJECTS AFTER ADVERSE EVENTS**

#### **5.4.1           Investigator Follow-Up**

The Investigator should follow each adverse event until the event has resolved to baseline grade or better, the event is assessed as stable by the Investigator, the subject is lost to follow-up, or the subject withdraws consent. Every effort should be made to follow all serious adverse events considered to be related to study drug or trial-related procedures until a final outcome can be reported.

During the study period, resolution of adverse events (with dates) should be documented on the Adverse Event eCRF and in the subject's medical record to facilitate source data verification. If, after follow-up, return to baseline status or stabilization cannot be established, an explanation should be recorded on the Adverse Event eCRF.

All pregnancies reported during the study should be followed until pregnancy outcome and reported according to the instructions provided in Section 5.3.3.

**RO7049389—F. Hoffmann-La Roche Ltd**  
61/Protocol YP39406, Version 4

#### **5.4.2 Sponsor Follow-Up**

For serious adverse events, non-serious adverse events of special interest, and pregnancies, the Sponsor or a designee may follow up by telephone, fax, electronic mail, and/or a monitoring visit to obtain additional case details and outcome information (e.g., from hospital discharge summaries, consultant reports, autopsy reports) in order to perform an independent medical assessment of the reported case.

#### **5.5 POST-STUDY ADVERSE EVENTS**

The Investigator is not required to actively monitor subjects for adverse events after the end of the adverse event reporting period (defined as 28 days after the last dose of study drug).

If the Investigator becomes aware of any other serious adverse event occurring after the end of the adverse event reporting period, if the event is believed to be related to prior study drug treatment the event should be reported directly to the Sponsor or its designee, either by faxing or by scanning and emailing the Serious Adverse Event Reporting Form using the fax number or email address provided to investigators.

#### **5.6 EXPEDITED REPORTING TO HEALTH AUTHORITIES, INVESTIGATORS, INSTITUTIONAL REVIEW BOARDS, AND ETHICS COMMITTEES**

The Sponsor will promptly evaluate all serious adverse events and non-serious adverse events of special interest against cumulative product experience to identify and expeditiously communicate possible new safety findings to investigators, IRBs, ECs, and applicable health authorities based on applicable legislation.

To determine reporting requirements for single adverse event cases, the Sponsor will assess the expectedness of these events using the following reference document:

- [RO7049389 Investigator's Brochure](#)

The Sponsor will compare the severity of each event and the cumulative event frequency reported for the study with the severity and frequency reported in the applicable reference document.

Reporting requirements will also be based on the investigator's assessment of causality and seriousness, with allowance for upgrading by the Sponsor as needed.

### **6. STATISTICAL CONSIDERATIONS AND ANALYSIS PLAN**

The primary objective of this study is to characterize the safety profile associated with a single dose and with multiple doses of RO7049389 in healthy volunteers. Statistical analyses will be descriptive in nature. Subjects will be grouped according to the actual treatment they received. All subjects who receive any amount of study medication (RO7049389 or matching placebo) and with at least one safety assessment will be

**RO7049389—F. Hoffmann-La Roche Ltd**

62/Protocol YP39406, Version 4

included in the safety analysis. All subjects who receive placebo will be combined into a single pooled placebo control group.

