## **2. OBJECTIVES**

### **2.1 PRIMARY OBJECTIVE**

The primary objective of this study is as follows:

- To assess the safety and tolerability of RO7049389 compared to placebo after single- and multiple-ascending oral doses in healthy Chinese subjects.

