## **6.1 DETERMINATION OF SAMPLE SIZE**

The sample size was determined by practical considerations and not based on statistical power calculations. Approximately four subjects will be enrolled in SAD cohort 1 (2 active treatment and 2 placebo). Approximately twelve subjects will be enrolled in each of the other SAD and MAD cohorts. They will be randomized to either active treatment (10 subjects per dose level) or placebo (2 subjects per dose level).

With ten subjects on active drug per dose group or cohort, there is a 94% chance to observe at least one AE that has an incidence rate of 25% in the population.

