## **6.2 SUMMARIES OF CONDUCT OF STUDY**

The number of study subjects who enroll, discontinue, or complete the study will be summarized by treatment (RO7049389 vs. matching placebo) for each dose cohort in the study. Reasons for premature study withdrawal will be listed and summarized by treatment and dose cohort. Enrollment and protocol deviations will be listed and evaluated for their potential impact on interpretation of study results. Study drug administration (RO7049389 or matching placebo) will be summarized with number of doses and percentage of assigned dose subjects received by treatment and dose cohort.

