## **6.4 SUMMARIES OF TREATMENT GROUP COMPARABILITY**

Study subjects randomized to receive placebo will be pooled together to form a pooled placebo group. Demographic and baseline characteristics (age, sex, etc.) will be summarized by treatment (each dose level of RO7049389 vs. pooled placebo group) for the safety population using descriptive statistics. For continuous variables, mean, standard deviation, median, and ranges will be presented. For categorical data, the

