### **6.5.1 Adverse Events**

The original terms recorded on the eCRF by the Investigator for adverse events will be standardized by the Sponsor.

Adverse events will be summarized by MedDRA coded term. In addition, adverse events will be summarized by their toxicity level (according to the maximum reported severity level) and severity (severe vs. non-severe). All serious adverse events, including deaths, severe adverse events (Grade  $\geq 3$ ), and adverse events of special interest will be listed and summarized separately. Adverse events leading to study drug discontinuation or interruption will be summarized as well. Subjects will be tabulated by treatment (RO7049389 vs. pooled placebo group) and dose level.

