### **6.5.2 Clinical Laboratory Test Results**

All clinical laboratory data will be stored on the database in the units in which they were reported. Study subject listings and summary statistics at each assessment time will be presented using the International System of Units (SI units; Système International d'Unités). Laboratory data not reported in SI units will be converted to SI units before processing.

Laboratory test values will be presented by individual listings with flagging of values outside the normal ranges.

The proportion of study subjects with laboratory abnormalities will be summarized by treatment (RO7049389 vs. pooled placebo group) and dose level. Additionally, the absolute value and change from baseline in all laboratory tests will be summarized by treatment and visit using descriptive statistics.

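### AE and laboratory-abnormality incidence is set against one study-wide placebo pool with no SAD/MAD split, so placebo is neither a single-dose nor a multiple-dose comparator

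*Combined protocol and SAP*

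**What the plan says.** Section 2.1 gives the primary objective: "To assess the safety and tolerability of RO7049389 compared to placebo after single- and multiple-ascending oral doses in healthy Chinese subjects". The opening of Section 6 restates it as being to "characterize the safety profile associated with a single dose and with multiple doses" of the drug.

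The pooling rule appears twice. Section 6 says "All subjects who receive placebo will be combined into a single pooled placebo control group", and Section 6.4 says "Study subjects randomized to receive placebo will be pooled together to form a pooled placebo group". Neither sentence mentions phase.

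Two incidence tables use the pool. For AEs, Section 6.5.1 says "Subjects will be tabulated by treatment (RO7049389 vs. pooled placebo group) and dose level". For laboratory abnormalities, Section 6.5.2 says "The proportion of study subjects with laboratory abnormalities will be summarized by treatment (RO7049389 vs. pooled placebo group) and dose level".

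Other summaries are cut differently. Section 6.2 says "Reasons for premature study withdrawal will be listed and summarized by treatment and dose cohort" and treats study drug administration the same way. Demographics are shown overall and by cohort (6.4), laboratory values and changes by visit (6.5.2), and ECG values by nominal time (6.5.4). None of these covers AE or laboratory-abnormality incidence.

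**The concern.** The objective poses two questions, and each needs its own placebo rate. Pooling placebo across cohorts within a phase is ordinary practice and is not at issue. This pool also merges different exposures:

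- Cohort 1 placebo subjects receive one dose (Section 3.1.1). So do Cohort 2 placebo subjects if that cohort's optional MAD part is not run (Table 1, footnote b).
- Subjects whose MAD part runs receive the single dose and then 14 days of dosing on the same allocation (Section 3.1.1.2).
- Replacements enrolled directly into MAD receive multiple doses only (Section 3.1.1).

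AE reporting runs from first study drug to 28 days after the last dose (Section 5.2.1), and Section 6 has no rule that assigns an event to SAD or MAD. The pooled incidence is therefore a weighted mix of the two phases, with weights that depend on which optional parts are run. These tables are the main output for the primary objective, and no inferential analysis stands beside them. If only the active columns are split by phase, placebo is watched for longer than the single-dose columns, and a single-dose excess could be hidden. If active subjects are counted over the whole study, the imbalance reverses for those who enter MAD.

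**Working it through.** **The plan's own figure.** Section 6.1 gives a 94% chance of at least one AE at 25% incidence in ten active subjects. 1 − 0.75^10 = 0.944, so it reproduces. It concerns active subjects only and does not bear on the placebo pool.

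**Who is in the pool.** Each cohort has 2 placebo subjects (Section 3.1.1). Table 1 ties Cohort 4 to an estimated efficacious dose of 400–600 mg q12h or higher, and Cohort 2 MAD to one below 400 mg q12h. Two scenarios fit both footnotes (replacements excluded):

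| | A: Cohort 2 MAD, no Cohort 4 | B: Cohort 4, no Cohort 2 MAD |
|---|---|---|
| Placebo pool | 6 (Cohorts 1–3) | 8 (Cohorts 1–4) |
| Single dose only | 2 (Cohort 1), 33% | 4 (Cohorts 1 and 2), 50% |
| Single dose plus MAD | 4 | 4 |
| One subject | 1/6 = 16.7 points | 1/8 = 12.5 points |

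**Exposure per placebo subject.**

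- Single dose only: 1 dose, 3 in-clinic nights (3.1.1.1) and 28 days of AE follow-up (3.1.1.1, 5.2.1).
- Both phases, q12h: 1 + 26 (Days 1–13) + 1 (Day 14, per 4.3.2.1) = 28 doses.
- Both phases, q24h: 1 + 14 = 15 doses.
- Both phases, nights: 3 + 16 = 19.
- Both phases, follow-up: about 14 days from the single dose to MAD start (about 1 week on SAD plus about 1 week washout; Synopsis, Length of Study) + 42 days for MAD = 56 days.

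**Mean follow-up in the pool.**

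- A: (2×28 + 4×56)/6 = 280/6 = 46.7 days
- B: (4×28 + 4×56)/8 = 336/8 = 42.0 days

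If MAD starts 7 days after the single dose (one reading of the minimum washout in Section 3.1.2), both phases take 49 days:

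- A: (2×28 + 4×49)/6 = 252/6 = 42.0 days
- B: (4×28 + 4×49)/8 = 308/8 = 38.5 days

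**Ratio of pooled placebo follow-up to an active column.**

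| Active column | A, 14 d | B, 14 d | A, 7 d | B, 7 d |
|---|---|---|---|---|
| Single dose, subject goes on to MAD (14 or 7 d) | 3.33 | 3.00 | 6.0 | 5.5 |
| Single dose, no MAD (28 d) | 1.67 | 1.50 | 1.5 | 1.38 |
| MAD only (42 d) | 1.11 | 1.00 | 1.0 | 0.92 |
| Whole study, entered MAD (56 or 49 d) | 0.83 | 0.75 | 0.86 | 0.79 |

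The first three rows apply if active columns are split by phase and the pool is not. The last applies if active subjects are counted over the whole study.

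**Illustration of the mixing, under assumed rates.** The documents give no placebo AE rates. Let pS and pM be the single-dose-phase and MAD-phase probabilities of at least one AE. A subject in both phases then has probability 1 − (1−pS)(1−pM), assuming independence. With pS = 10% and pM = 30% this is 1 − 0.9×0.7 = 0.37.

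- A: (2×0.10 + 4×0.37)/6 = 28.0%
- B: (4×0.10 + 4×0.37)/8 = 23.5%

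With 5% and 20% the pooled rates are 17.7% (A) and 14.5% (B). With 10% and 40% they are 34.0% and 28.0%. In every case the pooled rate matches neither input. These figures show the mechanism and are not an estimate of bias.

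**The case against.** The plan is silent on phase; it does not order the two phases to be merged. Section 6.1 counts 10 active and 2 placebo subjects per dose level in each SAD and MAD cohort, which suggests phase-specific dose levels. By Table 1, a Cohort 2 subject whose MAD part runs has 400 mg and then 200 mg q12h, and a Cohort 3 subject has 600 mg and then 400 mg q12h. Neither has one dose level across the study, so the active columns must be separated somehow. On this reading only a wording gap remains.

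It can also be said that the analysis is descriptive and the study was not sized on power, that all safety data are listed, and that splitting so few placebo subjects makes each rate coarser. Observation time matters more than the number of placebo doses, and pooled follow-up against a MAD column is nearly equal (0.92 to 1.11). Section 5.2.1 is a collection rule, so its lack of a phase boundary says nothing about table layout.

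Much of this stands as a limit on the size of the point. The active layout is indeed unstated, and the largest ratios need the 7-day assumption. It does not remove the point. If active columns must be phase-specific, the explicit rule for one placebo pool is what leaves them without a matching comparator. Near-equal follow-up does not make a pool that is one third to one half single-dose-only into a multiple-dose comparator. The cohort and visit splits elsewhere do not reach these tables, and a cohort split alone would not separate phases that the same subjects pass through.

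**Conclusion.** The concern holds. Followed as written, the pooling rule gives an AE and laboratory-abnormality placebo rate that answers neither half of the primary objective. One third (A) or one half (B) of the pool never has multiple doses. If the active columns are split by phase, pooled placebo follow-up is about three times that of a single-dose column of subjects who go on to MAD. With whole-study counting the ratio falls to 0.83 or 0.75 for active subjects who enter MAD.

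This rests on the planned 2 placebo subjects per cohort, no replacements, completion of planned follow-up, the Table 1 conditions for optional parts, and an interval of about 14 days from the single dose to MAD. Direction and size of distortion cannot be fixed without the table layout.

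The consequences are limited. Serious, severe and special-interest AEs are summarized separately (6.5.1), and escalation rests on review of individual data before each step (3.1.2, 3.1.2.1, 4.2.1). No error rate or sample-size figure changes. It should be corrected before the tables are programmed.

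**What to change.** In Sections 6, 6.4, 6.5.1 and 6.5.2, specify separate SAD and MAD tables for AE and laboratory-abnormality incidence, with placebo pooled across cohorts within each phase, and:

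- Label active columns by phase and regimen, since nominal doses such as 200 mg and 400 mg occur in both phases.
- Assign each AE to a phase by onset relative to the first MAD dose, with the same windows for active and placebo.
- Count subjects newly enrolled into MAD in the MAD tables only.
- For subjects with no MAD dose, either apply the same SAD window or show their full 28-day follow-up with the different window footnoted. The first option is cleaner, because the second leaves unequal windows within the SAD placebo group.

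The cost is SAP wording and table shells. AE start dates are already recorded, and design, dosing and sample size do not change. The SAD placebo group stays at 6 (A) or 8 (B), because every originally randomized placebo subject has the single dose. The drawback is a smaller MAD placebo group: 4 in either scenario, so one subject is 1/4 = 25 points. If the optional parts are run otherwise, it is 2 (Cohort 3 MAD only) to 6 (all MAD parts). The plan should state that group size beside the table.
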